APPENDIX D. MODIFIED (M)IWG-ERT-ECNM CRITERIA FOR OVERALL RESPONSES IN PATIENTS WITH ADVSM

Response Assessment	mIWG-MRT-ECNM Response Criteria
Complete remission (CR)*	
Requires all 4 of the following criteria and response duration must be ≥ 12 weeks:
 
No presence of compact neoplastic mast cell aggregates in the BM or other biopsied extracutaneous organ
 
Serum tryptase level < 20 ng/mL[†]
 
Peripheral blood count remission defined as: ANC $\geq 1 \times 10^9$/L with normal differential (absence of neoplastic mast cells and blasts $< 1\%$) and Platelet count $\geq 100 \times 10^9$/L and Hgb level ≥ 11 g/dL
 
Complete resolution of palpable hepatosplenomegaly and all biopsy-proven or suspected SM-related organ damage (C-findings)[‡]

CR with partial recovery of peripheral blood counts (CRh)*
 
Requires all criteria for CR be met and response duration must be ≥ 12 weeks; however, patient may have residual cytopenias.
	
Requires all criteria for CR be met and response duration must be ≥ 12 weeks; however, patient may have residual cytopenias. The following minimum recovery of peripheral blood counts is required:
 
ANC $> 0.5 \times 10^9$/L with normal differential (absence of neoplastic mast cells and blasts $< 1\%$) and Platelet count $> 50 \times 10^9$/L and Hgb level > 8.0 g/dL

Partial Remission (PR)*	
Requires all 3 of the following criteria, and response duration must be ≥ 12 weeks, in the absence of both CR and PD:
 
Reduction by $\geq 50\%$ in neoplastic mast cells in the BM and/or other extracutaneous organ at biopsy demonstrating eligible SM-related organ damage
 
Reduction of serum tryptase level by $\geq 50\%$[†]
 
Resolution of ≥ 1 biopsy-proven or suspected SM-related organ damage (C-finding[s])[‡]

Clinical Improvement (CI)*	
Response duration must be ≥ 12 weeks
 
Requires ≥ 1 of the nonhematologic and/or hematologic response criteria to be fulfilled in the absence of CR, CRh, PR, or PD

Stable disease (SD)	Not meeting criteria for CR, CRh, PR, CI, or PD
Progressive Disease (PD) [§]	Requires at least 1 element from the criteria below; duration must be ≥ 4 weeks:

Response Assessment **mIWG-MRT-ECNM Response Criteria**

	Baseline	Post-Baseline
	Any grade 2 non-hematologic organ damage	Worsening by 1 grade and minimum 100% increase (doubling) of laboratory abnormality
	≥Grade 2 albumin	Worsening by 1 grade and decrease by ≥0.5 g/dL
	≥Grade 3 nonhematologic organ damage	Minimum 100% increase (doubling) of laboratory abnormality
	≥Grade 2 transfusion-independent anemia or thrombocytopenia	New transfusion dependence of ≥4 units of RBCs or platelets at 8 weeks
	Transfusion-dependent anemia or thrombocytopenia	≥100% increase in the average transfusion frequency for an 8-week period compared with the 12 weeks preceding treatment
	≥Grade 3 neutropenia	>50% decrease in neutrophil count and Absolute decrease of neutrophil count of ≥0.25×10 ⁹ /L and Grade 4 (<0.5×10 ⁹ /L)
	Baseline spleen size ≤5 cm or not palpable	Development of at least 10 cm palpable symptomatic splenomegaly or Increase in spleen volume ≥25%
	Baseline splenomegaly >5 cm	>50% worsening and Development of ≥10 cm of palpable symptomatic splenomegaly compared with the baseline value or Increase in spleen volume ≥25%
Loss of response (LOR)	Loss of a documented CR, CR _h , PR, or CI or downgrading of CR/CR _h that must be for ≥8 weeks. Downgrading of CR to PR, or PR to CI is considered as such but is not considered a loss of response unless CI is also lost for ≥8 weeks. The baseline value for LOR is the pretreatment measurement(s) and not the nadir values during response.	

Abbreviations: ANC=absolute neutrophil count, BM=bone marrow, CI=clinical improvement, CR=complete recovery, CR_h=CR with incomplete hematologic recovery, Hgb=hemoglobin, IWG-MRT-ECNM=International Working Group-Myeloproliferative Neoplasms Research and Treatment European Competence Network on Mastocytosis, LOR=loss of response, MC=mast cell, mIWG-MRT-ECNM=modified International Working Group- Myeloproliferative Neoplasms Research and Treatment European Competence Network on Mastocytosis, PD=progressive disease, PR=partial response, RBC=red blood cell, SM=systemic mastocytosis.

- * Responses that are not maintained for a period of at least 12 weeks do not fulfill criteria for CR, PR, or CI; however, both maintained and unmaintained (<12 weeks duration) responses should be recorded each time they are observed in order to measure duration of response.
- † Only valid as a response criterion if the pretreatment serum tryptase level is ≥ 40 ng/mL (ie, if pretreatment serum tryptase is <40 ng/mL, it will not be considered as a criterion in evaluation of response).
- ‡ Biopsy of organ(s) in addition to the bone marrow to evaluate for SM-related organ damage may be considered.
- § Preservation of at least 1 CI finding permits a patient to maintain the response of CI if 1 or more CI findings are lost but none meet criteria for PD. However, if 1 or more of the CI findings become PD, then the CI finding assignment is lost and the patient meets criteria for PD. The baseline value for evaluating PD is the pretreatment measurement(s). The PD findings must be considered related to the underlying disease and not to other clinical factors. Progression of an underlying chronic myeloid neoplasm to acute myeloid leukemia is also considered PD.

Adapted from [NCCN Systemic Mastocytosis, Version 3.2021](#).

APPENDIX E. COMPARISON OF IWG-MRT-ECNM AND MODIFIED (M)IWG-MRT-ECNM RESPONSE CRITERIA FOR CLINICAL IMPROVEMENT (CI)

	IWG-MRT-ECNM Definition	IWG-MRT-ECNM Response Criteria	mIWG-MRT-ECNM Modifications
Non-hematologic C-Findings			
Ascites or pleural effusions	Symptomatic ascites or pleural effusion requiring medical intervention such as: Use of diuretics (grade 2) or ≥2 therapeutic paracenteses or thoracenteses (grade 3) at least 28 days apart over 12 weeks before the start of treatment with one procedure performed 6 weeks before the start of treatment	Complete resolution of symptomatic ascites or pleural effusion (including trace or minimal on radiographic imaging) and no longer in need of diuretics for ≥12 weeks and No longer in need of diuretics for ≥12 weeks or No therapeutic paracenteses or thoracentesis for ≥12 weeks	As IWG-MRT-ECNM
Liver function abnormalities	≥Grade 2 abnormalities in direct bilirubin ($>1.5 \times \text{ULN}$), AST ($>3.0 \times \text{ULN}$), ALT ($>3.0 \times \text{ULN}$), or ALP ($>2.5 \times \text{ULN}$) in the presence of: Ascites and/or Clinically relevant portal hypertension, and/or Liver MC infiltration that is biopsy-proven or No other identified cause of abnormal liver function	Reversion of ≥1 LFTs to normal range for ≥12 weeks	As IWG-MRT-ECNM
Hypoalbuminemia	≥Grade 2 hypoalbuminemia ($<3.0 \text{ g/dL}$)	Reversion of albumin to normal range for ≥12 weeks	As IWG-MRT-ECNM
Marked symptomatic splenomegaly	A spleen that is palpable >5 cm below the left costal margin and patient endorses symptoms of discomfort and/or early satiety	≥50% reduction in palpable splenomegaly (or ≥35% reduction in spleen volume based on 3D MRI or CT scan) and no endorsement of discomfort and/or early satiety for ≥12 weeks	Definition: Symptomatic or non-symptomatic splenomegaly palpable ≥5 cm below left costal margin. Response criteria: ≥35% reduction in spleen volume based

	IWG-MRT-ECNM Definition	IWG-MRT-ECNM Response Criteria	mIWG-MRT-ECNM Modifications
			on 3D MRI or CT scan for ≥ 12 weeks
Hematologic C-Findings			
Neutropenia	\geq Grade 3 ANC ($<1.0 \times 10^9/L$)	$\geq 100\%$ increase and an absolute increase $\geq 0.5 \times 10^9/L$ for ≥ 12 weeks	As IWG-MRT-ECNM
Anemia (transfusion-independent)	\geq Grade 2 Hgb (<10 g/dL)	An increase in Hgb ≥ 2 g/dL that is maintained for ≥ 12 weeks	As IWG-MRT-ECNM
Anemia (transfusion-dependent)	Transfusion of ≥ 6 units PRBCs in the 12 weeks before the start of treatment and Most recent transfusion occurring during the 4 weeks before the start of treatment and Transfusions administered for Hgb ≤ 8.5 g/dL and Reason for transfusions is not bleeding, hemolysis, or therapy-related	Transfusion independence for ≥ 12 weeks and maintenance of Hgb ≥ 8.5 g/dL at the end of the 12-week period of response duration	As IWG-MRT-ECNM
Thrombocytopenia (transfusion-independent)	\geq Grade 2 thrombocytopenia ($<75 \times 10^9/L$)	$\geq 100\%$ increase and an absolute increase $\geq 50 \times 10^9/L$ and no need for platelet transfusion for ≥ 12 weeks	As IWG-MRT-ECNM
Thrombocytopenia (transfusion-dependent)	Transfusion of ≥ 6 units of apheresed platelets during 12 weeks preceding treatment and ≥ 2 units transfused during 4 weeks preceding treatment and Transfusions administered for platelet count $<20 \times 10^9/L$	Transfusion independence for ≥ 12 weeks and maintenance of platelet count $\geq 20 \times 10^9/L$	As IWG-MRT-ECNM

Abbreviations: ALP=alkaline phosphatase, ALT=alanine aminotransferase, ANC=absolute neutrophil count, AST=aspartate aminotransferase, CT=computed tomography, Hgb=hemoglobin, IWG-MRT-ECNM=International Working Group-Myeloproliferative Neoplasms Research and Treatment European Competence Network on Mastocytosis, LFT=liver function test, MC=mast cell, mIWG-MRT-ECNM=modified International Working Group-Myeloproliferative Neoplasms Research and Treatment European Competence Network on Mastocytosis, MRI=magnetic resonance imaging, N/A=not applicable, PRBC=packed red blood cell, ULN=upper limit of normal.

CRh (CR with partial hematologic recovery) requires the following minimum levels for peripheral blood counts: absolute neutrophil count $\geq 0.5 \times 10^9/L$ with normal differential (absence of neoplastic mast cells and blasts $<1\%$) and platelet count $\geq 50 \times 10^9/L$ and hemoglobin ≥ 8.0 g/dL.

Adapted from: [Shomali et al, 2021](#).

APPENDIX F. COMPARISON OF IWG-MRT-ECNM AND MODIFIED (M)IWG-MRT-ECNM CRITERIA FOR RESPONSES IN PATIENTS WITH ADVSM

Response	IWG-MRT-ECNM Criteria for Response	mIWG-MRT-ECNM Modifications
Complete remission*	
Requires all 4 of the following criteria, and response duration must be ≥ 12 weeks:
 
 • No presence of compact neoplastic mast cell aggregates in the BM or other biopsied extracutaneous organ • Serum tryptase level < 20 ng/mL[†] • Peripheral blood count remission defined as: 
 ○ ANC $\geq 1 \times 10^9$/L with normal differential (absence of neoplastic mast cells and blasts $< 1\%$) and ○ Platelet count $\geq 100 \times 10^9$/L and ○ Hgb level ≥ 11 g/dL • Complete resolution of palpable hepatosplenomegaly and all biopsy-proven or suspected SM-related organ damage (C-findings)[‡] 	As IWG-MRT-ECNM
CR with partial recovery of peripheral blood counts*	Not included	
Requires all criteria for CR be met and response duration must be ≥ 12 weeks; however, patient may have residual cytopenias. The following minimum recovery of peripheral blood counts is required:
 
 • ANC $> 0.5 \times 10^9$/L with normal differential (absence of neoplastic mast cells and blasts $< 1\%$) and • Platelet count $> 50 \times 10^9$/L and • Hgb level > 8.0 g/dL
Partial remission*	
Requires all 3 of the following criteria, and response duration must be ≥ 12 weeks, in the absence of both CR and PD:
 
 • Reduction by $\geq 50\%$ in neoplastic mast cells in the BM and/or other extracutaneous organ at biopsy demonstrating eligible SM-related organ damage • Reduction of serum tryptase level by $\geq 50\%$[†] • Resolution of ≥ 1 biopsy-proven or suspected SM-related organ damage (C-finding[s])[‡] 	As IWG-MRT-ECNM

Response	IWG-MRT-ECNM Criteria for Response	mIWG-MRT-ECNM Modifications	
Clinical improvement*	Response duration must be ≥ 12 weeks Requires 1 or more of the nonhematologic and/or hematologic response criteria to be fulfilled in the absence of CR, PR, or PD	As IWG-MRT-ECNM, plus absence of CR/CRh	
Stable disease	Not meeting criteria for CR, PR, CI, or PD	Not meeting criteria for CR/CRh, PR, CI, or PD	
Progressive disease [§]	Requires at least one element from the criteria below; duration must be ≥ 8 weeks:		
	Baseline	Post baseline	
	Any grade 2 non-hematologic organ damage	Worsening by one grade and Minimum 100% increase (doubling) of laboratory abnormality	Elements are per IWG-MRT-ECNM
	\geq Grade 2 albumin	Worsening by one grade and Decrease by ≥ 0.5 g/dL	
	\geq Grade 3 non-hematologic organ damage	Minimum 100% increase (doubling) of laboratory abnormality	
	\geq Grade 2 transfusion-independent anemia or thrombocytopenia	New transfusion dependence at 8 weeks of ≥ 4 units of RBCs or platelets	
	Transfusion-dependent anemia or thrombocytopenia	$\geq 100\%$ increase in the average transfusion frequency for an 8-week period compared with the 12 weeks preceding treatment	
	\geq Grade 3 neutropenia	$>50\%$ decrease in neutrophil count and Absolute decrease of neutrophil count of $\geq 0.25 \times 10^9/L$ and grade 4 ($<0.5 \times 10^9/L$)	
	Baseline spleen size of not palpable or ≤ 5 cm	Development of at least 10 cm palpable symptomatic splenomegaly	
Splenomegaly >5 cm	$>50\%$ worsening and Development of ≥ 10 cm of palpable symptomatic splenomegaly compared with the baseline value	$>50\%$ worsening and Development of ≥ 10 cm of palpable symptomatic splenomegaly compared with the baseline value or Increase in spleen volume $\geq 25\%$	

Response	IWG-MRT-ECNM Criteria for Response	mIWG-MRT-ECNM Modifications
Loss of response	Loss of a documented CR, PR, or CI that must be for ≥ 8 weeks. Downgrading of CR to PR, or PR to CI is considered as such but is not considered a loss of response unless CI is also lost for ≥ 8 weeks. The baseline value for LOR is the pretreatment measurement(s) and not the nadir values during response.	As IWG-MRT-ECNM, plus loss or downgrading of CR/CRh

Abbreviations: ANC=absolute neutrophil count, BM=bone marrow, CI=clinical improvement, CR=complete recovery, CRh=CR with partial hematologic recovery, Hgb=hemoglobin, IWG-MRT-ECNM=International Working Group-Myeloproliferative Neoplasms Research and Treatment European Competence Network on Mastocytosis, LOR=loss of response, MC=mast cell, mIWG-MRT-ECNM=modified International Working Group-Myeloproliferative Neoplasms Research and Treatment European Competence Network on Mastocytosis, PD=progressive disease, PR=partial response, RBC= red blood cell, SM=systemic mastocytosis.

Guidelines for assessing response are as follows: (A) Only disease-related \geq grade 2 organ damage is evaluable as a primary endpoint. (B) Response assessments of CR, PR, SD, PD, and loss of response should only be applied to these \geq grade 2 organ damage findings in the context of trials. (C) Disease status at the time of patient removal from the study singularly relates to the updated status of initial \geq grade 2 organ damage finding(s). (D) Exclusion of drug-related toxicity and/or other clinical issues (e.g., gastrointestinal tract bleeding in the case of worsening anemia/transfusion-dependence) should be undertaken before assigning the designation PD or loss of response in a patient with worsening of baseline \geq grade 2 organ damage.

* Responses that are not maintained for a period of at least 12 weeks do not fulfill criteria for CR, PR, or CI; however, both maintained and unmaintained (<12 weeks duration) responses should be recorded each time they are observed in order to measure duration of response.

† Only valid as a response criterion if the pretreatment serum tryptase level is ≥ 40 ng/mL (i.e., if pretreatment serum tryptase is <40 ng/mL, it will not be considered as a criterion in evaluation of response).

‡ Biopsy of organ(s) in addition to the bone marrow to evaluate for SM-related organ damage may be considered.

§ Preservation of at least one CI finding permits a patient to maintain the response of CI if one or more CI findings are lost but none meet criteria for PD. However, if one or more of the CI findings become PD, then the CI finding assignment is lost and the patient meets criteria for PD. The baseline value for evaluating PD is the pretreatment measurement(s). The PD findings must be considered related to the underlying disease and not to other clinical factors. Progression of an underlying chronic myeloid neoplasm to acute myeloid leukemia is also considered PD.

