Radiological Evaluations - MRI/CT abdomen/pelvis - Skeletal imaging (as appropriate)	Refer to Table 3 Schedule of Response Assessments.																					
Spleen palpation	Refer to Table 3 Schedule of Response Assessments.																					
QOL assessments (m)		X							X				X				X		X			
MAS (n)	X							X				X		X				X	X			
Bezuclastinib administration (o)	Daily through Cycle (a)																					
Study drug diary (p)		X							X				X (a)		X (a)		X (a)					
Overall response assessment	Refer to Table 3 Schedule of Response Assessments																					
AE monitoring (q)	X	X																				

Table 1: Schedule of Assessments and Procedures

	Screening	Cycle 1							Cycle 2				Cycles 3-15 (a, b)		Even-Numbered Cycles (C16+ beyond) (a, b)		Odd-Numbered Cycles (C17+ beyond) (a, b)		EOT (c)	SFU	Long-Term Follow-Up
Study Day	-42 to -1	1	2	4*	8	11*	15	22	1	8*	15	22*	1	22	1	22	1	22		30 d after last dose	Every 3 months after SFU
Window (Days)				±1	±2	±1	±2	±2	±2	±2	±2	±2	±3	±3	±3	±3	±3	±3		±7	±7
Concomitant medications (q)	X	X																			
Survival status (r)																					X
Disease status (s)																					X

Abbreviations: AE=adverse event, C=Cycle, CT=computed tomography, D/d=day, ECG=electrocardiogram, ECOG=Eastern Cooperative Oncology Group, eCRF=electronic case report form, EOT=end of treatment, HCV=hepatitis C virus, ICF=informed consent form, IWG-MRT-ECNM=International Working Group-Myeloproliferative Neoplasms Research and Treatment European Competence Network on Mastocytosis, MAS=Mastocytosis Activity Score, MRI=magnetic resonance imaging, PBS=peripheral blood smear, PE=physical examination, PK=pharmacokinetic, QOL=quality of life, SAE=serious adverse event, SFU=Safety Follow-up, TEAE=treatment-emergent adverse event.

One cycle = 28 days.

Standard of care assessments or procedures that may confirm study eligibility requirements may be performed prior to a subject signing the ICF.

On-treatment assessments and sample collections will be performed prior to dosing with study drug and, as applicable, prior to ECG for scheduled visits involving study drug administration and/or ECGs, unless otherwise noted. Additional assessments to evaluate subject safety and efficacy may be performed at unscheduled visits and will be recorded in the eCRFs.

* Additional hematology and chemistry assessments to be performed for subjects in Part 1 and Part 2 Stage 1 only.

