(a) After 15 cycles, dispensation of study drug for at-home administration and study drug diary will be adjusted accordingly.

(b) At C15 and beyond, and at most other study visits, clinical chemistry, hematology, pregnancy testing (women of childbearing potential only), AE monitoring, and collection of concomitant medications will be performed.

(c) EOT assessments should be performed within 7 days of decision to permanently discontinue study treatment.

(d) Subjects should be dosed as soon as possible after randomization and preferably within 7 days before receiving their first dose on C1D1.

(e) A complete PE will be performed at Screening only. At all other study visits, a targeted PE will be performed based on Investigator’s judgment and careful evaluation of the subject’s signs and symptoms.

- (f) Height at Screening only.
- (g) A single 12-lead ECG will be performed after the subject has been resting in supine or semi-supine position for at least 5 minutes. At all predose and postdose intervals, each ECG should occur just prior to each PK blood sample collection.
- (h) On C1D1 and C2D1, a single ECG will be performed predose (within 30 min prior to dosing) and at 1 (\pm 5 minutes), 3 (\pm 15 minutes), 5 (\pm 15 minutes), and 8 (\pm 30 minutes) hours postdose.
- (i) Safety laboratory tests (hematology, chemistry) may be completed 1 day prior to the visit on C1D1 (after randomization) or on C2D1.
- (j) Serum tryptase will be collected as indicated and at all response time points. Serum tryptase will be tested locally. A blood sample will also be collected and tested at a central laboratory. Additional exploratory analyses may be performed on blood samples to further explore pharmacodynamic markers in subjects with AdvSM.
- (k) Subjects with a positive HCV antibody may be eligible if HCV RNA is undetectable on a quantitative HCV RNA assay, following discussion with the Medical Monitor.
- (l) Women of childbearing potential only. A serum pregnancy test (β -human chorionic gonadotropin) will be performed at Screening, and a urine pregnancy test will be performed at subsequent visits.
- (m) QOL assessments to include Patient Global Impression of Severity (PGIS), Patient Global Impression of Change (PGIC), and the Mastocytosis Quality of Life Questionnaire (MC-QoL). PGIC will be performed starting on C2D1.

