 - (f) Photography assessments for skin or other clinically relevant lesions will be repeated every 3 cycles (as applicable) if skin lesions are present at Screening or develop during the treatment period, per Investigator discretion. After 12 cycles, photography assessments will be performed every 6 cycles and as clinically indicated.
 - (g) Overall response assessment will be performed at C3D1, and every 3 cycles thereafter beginning at C6D1 (C6, C9, C12), and then every 6 cycles (C18, C24, etc) thereafter and as clinically indicated and during the 12-week confirmation of response, as applicable. If an initial response (CR, CRh, PR, or CI) is achieved on or after C12, an overall response assessment will be performed 12 weeks after the initial documented response to confirm response per modified IWG-MRT-ECNM response criteria.

SPECIAL CONSIDERATION FOR THE USE OF REMOTE VISITS

When necessary and appropriate, investigative sites may use telemedicine visits, using adequate audio and video equipment, to interact with subjects to make health assessments in the home for the purpose of augmenting care, assessing emerging or existing adverse events, adjusting concomitant medications, or arranging for study-related local laboratory assessments.

If needed, due to subject/site circumstances such as COVID-19, study safety laboratory assessments may be obtained at a laboratory closer to the subject's home per the discretion of the treating physician and with approval from the Sponsor. The laboratory assessments should be reviewed, and appropriate follow-up should be completed per protocol and standard of care. The normal limits for laboratory findings for such laboratory assessments should be included in the subject's health records and recorded on the appropriate electronic case report form (eCRF). If alternative laboratories are used frequently, additional paperwork may be required for the study files and databases in accordance with regulations. Please discuss with the Medical Monitor and/or Sponsor.

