3.1.4. Response Assessments

A bone marrow assessment will be performed on Cycle 3 Day 1 to document initial response. Bone marrow assessments will be performed every 3 cycles (approximately every 12 weeks) from Cycle 6 until Cycle 12 (Day 1 of C6, C9, C12), and then every 6 cycles (C18, C24, etc.) thereafter. If an initial response (CR, CRh, PR, or CI) is achieved on or after C12, a repeat bone marrow assessment will be performed 12 weeks after the initial documented response to confirm response per modified IWG-MRT-ECNM response criteria. Changes in liver and spleen size will be assessed by MRI and palpation. A computed tomography scan may be used if MRI cannot be performed. Skeletal imaging is required at Screening for all subjects to assess for baseline lytic lesions and/or pathologic fractures. Changes in the size of bony lesions will be assessed with skeletal imaging. Refer to [Section 6.15](#) for further information regarding disease assessments.

[figure not shown]

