6.3. ENROLLMENT

Enrollment will take place before the start of study drug administration. Once a subject has given written informed consent, the Investigator will commence all screening assessments. An Interactive Response Technology (IRT) system will be used for enrollment, randomization (in Part 1 and Part 2 Stage 1), and drug management. After all screening assessments have been completed and the EC has approved enrollment into the study, the IRT will assign each subject a Subject Identification Code.

The diagnosis and evidence of measurable disease must be evaluable according to response criteria and confirmed by the EC prior to randomization in Part 1 and Part 2 Stage 1 and prior to the first dose of study drug in Part 2 Stage 2. The EC will consist of a pathologist and at least 1 clinician who is skilled in the diagnosis and treatment of mastocytosis. The requirement for measurable disease is intended to ensure the eligibility of all subjects in Part 1 and Part 2 who are evaluable for response per modified IWG-MRT-ECNM criteria. The study allows for a subset of subjects in both Part 1 and Part 2 with AdvSM who are not evaluable per modified IWG-MRT-ECNM response criteria based on a lack of evaluable organ damage.

Subjects can be rescreened up to 2 times, at a maximum total of 3 screens, each screen consisting of all screening assessments and EC review.

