8.4.4. Response-Evaluable Analysis Set

The Response-Evaluable Analysis Set includes subjects who are evaluable per modified IWG-MRT-ECNM criteria who enrolled in the study at least 20 weeks before the data cutoff, ie, all subjects enrolled within 20 weeks will be excluded from the analysis regardless of study discontinuation status. The minimum required follow up time to observe a confirmed response is 20 weeks. This analysis set will be used when not all subjects have been followed long enough to observe a confirmed response.

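### A response must last at least 84 days, but response visits from C3 to C12 are nominally exactly 84 days apart with ±3-day windows, and the 20-week rule in Section 8.4.4 leaves no slack

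*Protocol*

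**What the plan says.** **Response definition.** In Appendix D, CR, CRh, PR and CI each carry a minimum duration of 12 weeks. The footnote to the table adds: "Responses that are not maintained for a period of at least 12 weeks do not fulfill criteria for CR, PR, or CI". No tolerance in days is stated.

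**Visit schedule.** Section 3.1.4 begins with C3: "A bone marrow assessment will be performed on Cycle 3 Day 1 to document initial response". It continues "every 3 cycles (approximately every 12 weeks) from Cycle 6 until Cycle 12". Table 3 footnote (g) sets the same rhythm for the overall response: "Overall response assessment will be performed at C3D1, and every 3 cycles thereafter beginning at C6D1 (C6, C9, C12". The notes to Table 1 state "One cycle = 28 days", and treatment runs without gaps between cycles. The window row of Table 1 gives ±3 days for Day 1 of Cycles 3-15. Table 3 has no window row.

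**Confirmation visits.** Section 3.1.4 and Table 3 footnotes (c), (d) and (g) add a separate 12-week repeat only when the first response is seen at C12 or later. Section 6.15.1 asks for a repeat marrow 12 weeks after a response, without the C12 restriction and without a window.

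**Response-Evaluable set.** Section 8.4.4 admits evaluable subjects enrolled at least 20 weeks before the data cutoff, because "The minimum required follow up time to observe a confirmed response is 20 weeks". Section 6.3 says "Enrollment will take place before the start of study drug administration". Table 1 footnote (d), attached to randomization, places dosing soon after it, "preferably within 7 days before receiving their first dose on C1D1".

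**The concern.** The minimum duration and the visit spacing are the same number of days, and the window runs in both directions. If the first visit is a little late or the second a little early, the pair is shorter than 84 days although both visits comply with the protocol. Read literally, the response is then unconfirmed at C6 and waits for C9. If the adjudicators read 12 weeks loosely, it counts. The primary endpoint is confirmed ORR as assessed by the CRRC in an open-label trial, so this should not be settled subject by subject.

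The 20 weeks in Section 8.4.4 is built on the same C3-to-C6 pair, but the clock starts at enrollment, which precedes dosing. The set is meant to hold subjects followed long enough for a confirmed response to be observable. As defined, it can include some whose confirming visit has not come due, and they count as non-responders.

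**Working it through.** **Inputs.** Cycle length 28 days (Table 1 notes). Response visits on Day 1 of C3, C6, C9 and C12 (Section 3.1.4, Table 3). Window ±3 days (Table 1). Minimum duration 84 days (Appendix D). Windows are taken around the nominal date counted from C1D1.

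**1. The plan's 20 weeks.**
- C3D1 = 2 × 28 = day 56 after first dose (week 8).
- C6D1 = 5 × 28 = day 140 (week 20).
- Gap = 140 − 56 = 84 days = 12 weeks.

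The 20 weeks reproduces, counted from first dose and with no slack.

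**2. Range of compliant gaps.** Let d3 and d6 be the day offsets of the two visits, each from −3 to +3. Gap = 84 + d6 − d3.
- Smallest: 84 − 3 − 3 = 78. Largest: 84 + 3 + 3 = 90.
- The gap is short whenever d6 < d3, by 1 to 6 days.

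This step needs no assumption about how visits are distributed.

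**3. How often a pair is short.** The documents give no distribution of visit days. If the two offsets are independent with the same distribution, P(d6 < d3) = (1 − P(d6 = d3)) / 2.

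| Assumed visit days | P(gap under 84 days) |
|---|---|
| All on the nominal day | 0% |
| 90% on the day, rest spread evenly | 9% |
| 70% on the day, rest spread evenly | 25% |
| 50% on the day, rest spread evenly | 35% |
| Triangular (weights 1, 2, 3, 4, 3, 2, 1) | 41% |
| Uniform on 7 whole days | (1 − 7/49)/2 = 21/49 = 42.9% |
| Continuous uniform | 50% |

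These are shares of visit pairs, not of responders who lose confirmation.

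**4. What happens to a short pair.** C9D1 = 8 × 28 = day 224 (week 32). The C3-to-C9 gap is at least 168 − 6 = 162 days, so a response still present at C9 meets the 84 days easily. Confirmation moves from about week 20 to about week 32.

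**5. Section 8.4.4.** The latest in-window C6D1 is 140 + 3 = day 143 from first dose, before any lag from enrollment to dosing is added. As an illustration for the randomized parts, a 7-day lag gives 143 + 7 = 150 days (21.4 weeks) after enrollment, against the 140 days required. Even counted from first dose, under the uniform assumption only the pairs with d3 ≤ d6 ≤ 0 are both long enough and complete by day 140. That is 10/49 = 20%.

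**6. Check of the remedies.**
- Confirming visit 84 to 90 days after the actual first date: no short pairs. Latest confirmation = 56 + 3 + 90 = day 149 from first dose (21.3 weeks).
- A fixed tolerance accepting 78 days or more: 0 of 49 pairs fall short. Latest confirmation = day 143.
- Moving only the C6 window to 0/+6 days from its nominal date: 6/49 = 12% still fall short, so this does not work.

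**The case against.** The strongest reply is that little is lost, and most of that reply stands.

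- **Primary analysis.** Confirmed ORR is analysed in the ITT set, and treatment continues until progression, toxicity or another listed reason. A lasting response that misses at C6 is confirmed at C9.
- **Stopping between C6 and C9.** Table 3 schedules marrow, imaging, spleen palpation and overall response at end of treatment. The marrow is waived only if one was taken within 7 days. Most subjects who stop while still responding therefore get a further full assessment.
- **Laboratory-based CI.** Hematology and chemistry are drawn every cycle through C15, so the duration of albumin, liver-test or blood-count improvement need not rest on the C3 and C6 visits alone. CR, CRh, PR and spleen volume are the exposed elements.
- **Section 6.15.1.** It can be read as timing the repeat marrow from the actual response date at any cycle. But it gives no window and does not require a minimum of 12 weeks, whereas the same section sets minimum intervals for confirming progression and loss of response. It also sits beside a Section 3.1.4 that limits the dedicated repeat to C12 and later.
- **Day counting elsewhere.** A CRRC charter or the SAP, neither at hand, may fix a tolerance, and Section 3.1.4 calls the spacing approximate. Appendix D as written allows none.

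A reader might infer that 43% of responders go unconfirmed. The documents do not support that: the figure is a share of visit pairs under one assumed distribution. A reader might also carry it into the Stage 2 test, as 60% × 28/49 = 34.3% ORR. That would need every responder to be first seen at C3 and no assessment to count after C6, which the ITT analysis and the schedule rule out. Nor is 150 days a Stage 2 figure or a maximum. The 7 days is only a preference, and it is attached to randomization, which Stage 2 does not have.

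**Conclusion.** The conflict is in the text. A strict 84-day minimum is paired with visits nominally 84 days apart and a symmetric window, so a subject fully on schedule can miss the definition by 1 to 6 days. The share of C3-to-C6 pairs affected is unknown: 43% under independent uniform visit days, 0 to 50% across the distributions tried.

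The effect on the primary ITT ORR is mostly delay. Actual loss is limited to subjects who lose response, or stop without a usable end-of-treatment assessment, soon after a short C3-to-C6 pair, and whose response rests on marrow or imaging. The documents give no basis for sizing that group, and nothing here shows that the Stage 2 test is compromised.

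Section 8.4.4 starts its clock at the wrong event and omits the window. The result is a small downward bias in the Response-Evaluable set only, depending on how many subjects were enrolled shortly before the 20-week limit at a given cutoff. Both points are worth correcting because the remedy is wording, and it takes a judgement about day counting out of the adjudication of the primary endpoint.

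**What to change.** 1. **Confirming visit.** In Table 3 footnotes (c), (d) and (g) and in Section 6.15.1, schedule the confirming assessment 84 to 90 days after the actual date of the first qualifying assessment, replacing the ±3-day window for that visit. Appendix D stays unchanged. If the sponsor prefers to keep the existing windows, state one fixed day tolerance for 12 weeks in advance. Accepting 78 days or more covers every in-window pair, but it makes the responder definition slightly easier to meet in a single-arm comparison with a historical rate, so the first option is preferable.
2. **Section 8.4.4.** Count from first dose and include the window: at least 149 days (22 weeks in whole weeks) with the 84-to-90-day rule, or at least 143 days (20 weeks + 3 days) if a tolerance is used.

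**Cost.** Wording changes, with the CRRC charter aligned; no added procedures. Some confirming visits are booked a few days later, and the Response-Evaluable set is slightly smaller at an early cutoff.
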